4.6 Additional Requirements

- 4.6.1 Patients must provide a signed and dated, written informed consent form.

**NOTE:** Copies of the consent are not collected by the ECOG-ACRIN Operations Office – Boston.

- 4.6.2 The IRB-approved consent must allow patients the option to provide specimens to for use in undefined future research.
- 4.6.3 Biological samples to be submitted as indicated in Section [11](#).
- 4.6.4 Imaging studies are to be submitted as outlined in Section [10](#).
- 4.6.5 Data collection for this study will be done exclusively in Medidata Rave. Study staff will receive an invitation to join the study in Rave

after evidence of IRB approval is submitted to RSS. Access to the trial in Rave is granted through the iMedidata application to all persons with the appropriate roles in RSS after IRB approval is obtained. To access iMedidata/Rave the site user must have an active CTEP IAM account (<https://eapps-ctep.nci.nih.gov/iam>). In addition, site users that are a member of ECOG-ACRIN must have the mapped ECOG-ACRIN roles or explicit Rave roles (Rave CRA, Read-Only, Site Investigator) in RSS at the enrolling site. Site users that are not members of ECOG-ACRIN must have the Rave roles on the CTSU roster at the enrolling sites. The Site Administrator or Data Administrator at the enrolling site may assign the appropriate roles from the Site Roles tab on the CTSU website.

Upon initial site registration approval for the study in RSS, all persons with Rave roles assigned on the appropriate roster will be sent study invitation e-mails from iMedidata. To accept the invitation, site users must log into the Select Login (<https://login.imedidata.com/selectlogin>) using their CTEP-IAM user name and password, and click on the “accept” link in the upper right-corner of the iMedidata page. Please note, site users will not be able to access the study in Rave until all required Medidata and study specific trainings are completed. Trainings will be listed in the upper right pane of the iMedidata screen.

Users that have not previously activated their iMedidata/Rave accounts will also receive a separate invitation from iMedidata to activate their account. Account activation instructions are located on the CTSU website, Rave tab under the Rave resource materials (Medidata Account Activation and Study Invitation Acceptance). Additional information on iMedidata/Rave is available on the CTSU website under the Rave tab at [www.ctsu.org/RAVE/](http://www.ctsu.org/RAVE/) or by contacting the CTSU Help Desk at [name] or by e-mail at [[contact]](mailto:[contact]).

#### 4.7 Instructions for Patients who Do Not Start Assigned Protocol Treatment

If a patient does not receive any assigned protocol treatment, baseline and follow-up data will still be collected and must be submitted according to the instructions in the E2211 Forms Completion Guidelines.

Rev. 7/15

## 5. Treatment Plan

### 5.1 Administration Schedule

One cycle = 28 days

All doses are based on actual weight. If there is a  $< 5\%$  change in Body Surface Area (BSA), keep the doses the same. If there is a  $\geq 5\%$  change in BSA, a new dosing weight and BSA should be set and used for dose calculations.

- Temozolomide
  - The temozolomide dose will be capped at 400 mg daily. The calculated dose by BSA will be rounded down to minimize the number of capsules required. The treating investigator should use their best judgment to meet these guidelines.
  - Temozolomide should be taken by mouth at night after fasting from solid food for two hours. Temozolomide capsules must not be crushed and must be administered whole.
  - Temozolomide missed doses will not be made up and patients should not double-up on missed doses during treatment.
  - Ondansetron or other anti-emetic is strongly suggested as a premedication 30-60 minutes prior to temozolomide. Otherwise, anti-emetics, anxiolytics, and analgesics may be provided at physicians' discretion.
- Capecitabine
  - The calculated total daily capecitabine dose by BSA will be rounded down to allow doses using 500 mg tablets. Investigators should approximate the calculated dose based on the pill size available while rounding down to minimize the number of capsules required. The treating investigator should use their best judgment to meet these guidelines.
  - Capecitabine should be taken morning and night, with at least 8 hours between each dose. Capecitabine tablets should be swallowed with water within 30 minutes after a meal.
  - Capecitabine missed doses will not be made up and patients should not double-up on missed doses during treatment.

**NOTE:** Monitor CBC and platelet count prior to drug administration.

#### 5.1.1 ARM A

Temozolomide 200 mg/m^2 po QD days 1-5

Repeat cycles every 28 days

Maximum duration of treatment 13 cycles (approximately 1 year)

#### 5.1.2 ARM B

Capecitabine 750 mg/m^2 po BID days 1-14

Temozolomide 200 mg/m^2 po QD days 10-14

Repeat cycles every 28 days

Maximum duration of treatment 13 cycles (approximately 1 year)

## 5.2 Adverse Event Reporting Requirements

### 5.2.1 Purpose

Adverse event (AE) data collection and reporting, which are required as part of every clinical trial, are done to ensure the safety of the patients enrolled, as well as those who will enroll in future studies using similar agents.

**Routine reporting:** Adverse events are reported in a routine manner at scheduled times during the trial using Medidata Rave.

**Expedited reporting:** In addition to routine reporting, certain adverse events must be reported in an expedited manner for timelier monitoring of patient safety and care. The following sections provide information and instructions regarding expedited adverse event reporting.

### 5.2.2 Terminology

- **Adverse Event (AE):** Any untoward medical occurrence associated with the use of a drug in humans, whether or not considered drug related. Therefore, an AE can be **ANY** unfavorable and unintended sign (including an abnormal laboratory finding), symptom, or disease temporally associated with the use of a medicinal product, whether or not considered related to the medicinal product.
- **Attribution:** An assessment of the relationship between the adverse event and the protocol treatment, using the following categories.

ATTRIBUTION	DESCRIPTION
Unrelated	The AE is clearly NOT related to treatment
Unlikely	The AE is doubtfully related to treatment
Possible	The AE may be related to treatment
Probable	The AE is likely related to treatment
Definite	The AE is clearly related to treatment

- **CTCAE:** The NCI Common Terminology Criteria for Adverse Events provides a descriptive terminology that is to be utilized for AE reporting. A grade (severity) is provided for each AE term.
- **Expectedness:** Any adverse event, the type or severity of which is consistent with the current investigator's brochure, product label, and/or the protocol document

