#### 5.2.4 Determination of reporting requirements

Many factors determine the reporting requirements of each individual protocol, and which events are reportable in an expeditious manner, including:

- the phase (0, 1, 2, or 3) of the trial
- whether the patient has received an investigational or commercial agent or both
- the Common Terminology Criteria for Adverse Events (CTCAE) grade
- the relationship to the study treatment (attribution)
- the expectedness of the adverse event

**Using these factors, the instructions and tables in the following sections have been customized for protocol E2211 and outline the specific expedited adverse event reporting requirements for study E2211.**

5.2.5 Steps to determine if an adverse event is to be reported in an expedited manner

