5.2.6 Expedited Reporting Requirements for Arms A and B on protocol E2211

Commercial Agents: Temozolomide and Capecitabine

Expedited reporting requirements for adverse events experienced by patients on arm(s) with commercial agents only – (Arms A and B)					
Attribution	Grade 4		Grade 5 a		ECOG-ACRIN and Protocol-Specific Requirements
	Unexpected	Expected	Unexpected	Expected	
Unrelated or Unlikely			7 calendar days	7 calendar days	See footnote (b) for special requirements.
Possible, Probable, Definite	7 calendar days		7 calendar days	7 calendar days	

**7 Calendar Days:** Indicates a full CTEP-AERS report is to be submitted within 7 calendar days of learning of the event.

**a** This includes all deaths within 30 days of the last dose of treatment regardless of attribution. **NOTE: Any death that occurs > 30 days after the last dose of treatment and is attributed possibly, probably, or definitely to the treatment must be reported within 7 calendar days of learning of the event.**

**b** Protocol-specific expedited reporting requirements: The adverse events listed below also require expedited reporting for this trial:

**Serious Events:** Any event following treatment that results in *persistent or significant disabilities/incapacities, congenital anomalies, or birth defects* must be reported via CTEP-AERS within 7 calendar days of learning of the event. For instructions on how to specifically report these events via CTEP-AERS, please contact the AEMD Help Desk at [[contact]](mailto:[contact]) or [contact]. This will need to be discussed on a case-by-case basis.

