8.2.10 Side Effects

Hematologic: anemia, neutropenia, thrombocytopenia  
Cardiovascular: Edema, venous thrombosis  
Constitutional: fatigue, pyrexia, swelling in hands, feet or abdomen, pain, chest pain  
Dermatologic: hand-foot syndrome, dermatitis, skin discoloration, alopecia  
Gastrointestinal: diarrhea, nausea, vomiting, stomatitis, abdominal pain, gastrointestinal motility disorder, constipation, taste disturbance, upper GI inflammatory disorders, gastrointestinal hemorrhage, ileus  
Hepatic: hyperbilirubinemia  
Infections: bacterial or viral  
Metabolic: appetite decreased, dehydration  
Musculoskeletal: back pain, arthralgia  
Neurologic: peripheral sensory neuropathy, headache, dizziness, insomnia  
Ocular: eye irritation, vision abnormal  
Psychiatric: mood alteration, depression  
Pulmonary: dyspnea, cough, pharyngeal disorder, epistaxis, sore throat  
Vascular: venous thrombosis

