#### 9.4 Safety Monitoring

Interim analyses of toxicity are performed twice yearly for all ECOG-ACRIN studies. Expedited reporting of certain adverse events is required through the CTEP-AERS system, which is monitored continuously with formal notifications monthly of unexpected grade 4 and 5 events. Formal comparison of toxicity rates between the arms is not a goal of this trial and the sample size will provide sufficient power for detecting only relative large difference in adverse events. With at least 69 patients per treatment arm, a 90% confidence interval on any adverse event rate will be no wider than 21 percentage points and there is at least 87% probability of observing one or more rare events (3% true probability) in either treatment arm.

Reports of these analyses are sent to the ECOG-ACRIN Principal Investigator or Senior Investigator at the participating institutions. Expedited reporting of certain adverse events is required, as described in Section [5](#).

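### Section 5.2.2 calls an event expected if its type or its severity matches the references, so a related grade 4 event of listed type but undescribed severity needs no expedited report

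*Combined protocol and SAP*

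**What the plan says.** Section 5.2.2 opens its definition of expectedness with "Any adverse event, the type or severity of which is consistent with the current"; the references it then names are the brochure, the label and the protocol, joined by and/or. The same section treats severity as an attribute separate from the event term; on the CTCAE it says "A grade (severity) is provided for each AE term".

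Section 5.2.4 lists the factors that decide whether an event is expedited, and one of them is "the expectedness of the adverse event".

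Section 5.2.6 applies this in a table headed "Expedited reporting requirements for adverse events experienced by patients on arm(s) with commercial agents only". In the row labelled "Possible, Probable, Definite", grade 4 unexpected carries a 7-calendar-day report and grade 4 expected is blank. Both grade 5 cells are filled.

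Section 5.2.7 requires the institution to report to its IRB those events that are reportable through CTEP-AERS, and ECOG-ACRIN forwards the CTEP-AERS reports to the regulatory agencies. Section 9.4 says that CTEP-AERS is "monitored continuously with formal notifications monthly of unexpected grade 4 and 5 events".

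The protocol's own reference lists, 8.1.10 for temozolomide and 8.2.10 for capecitabine, name types of event without grades. The gastrointestinal entry for capecitabine, for instance, ends "upper GI inflammatory disorders, gastrointestinal hemorrhage, ileus", with no severity attached to any term.

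**The concern.** Expedited reporting exists, as 5.2.1 puts it in substance, so that patient safety can be watched more promptly than routine reporting allows. An event of a known type appearing at a severity not described before is one of the signals such a channel should carry. Under the *or* rule the known type alone makes the event expected, and the new severity does not count.

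Three things depend on that classification: the 7-day report itself, the monthly notifications in 9.4, and the onward reporting in 5.2.7. A site that follows 5.2.2 to the letter would leave the event out of all three. A site that assumes the definition means both attributes would include it. Two sites could therefore handle the same event differently, and each could defend its choice.

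**Working it through.** No sample size, power or alpha figure depends on this point, so the check is one of logic.

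**Step 1: the rule.** As written in 5.2.2, expected = (type consistent) OR (severity consistent). The complement is unexpected = (type not consistent) AND (severity not consistent). No other section that can be read defines unexpected or alters the connective.

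**Step 2: apply it to a grade 4 event with possible, probable or definite attribution in the 5.2.6 table.**

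| Type consistent with references | Severity consistent with references | As written (*or*) | Report as written | With *and* | Report with *and* |
|---|---|---|---|---|---|
| Yes | Yes | Expected | None | Expected | None |
| Yes | No | Expected | None | Unexpected | 7 days |
| No | Yes | Expected | None | Unexpected | 7 days |
| No | No | Unexpected | 7 days | Unexpected | 7 days |

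A report is required in 1 of 4 combinations as written, and in 3 of 4 with *and*. These are counts of combinations, not of events. The second row is the one that matters in practice. The third row follows from the literal wording, although a severity that matches without a matching type has little practical meaning.

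**Step 3: where the second row can arise.** Section 5.2.2 accepts consistency with the brochure, the label and/or the protocol. Sections 8.1.10 and 8.2.10 are part of the protocol and give types only, so any type on either list meets the type condition without saying anything about grade. The connective then changes the outcome only if grade 4 for that type is also undescribed in the label and the brochure. If a reference does describe grade 4, the event is in the first row and *or* and *and* agree.

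**Step 4: what follows for a second-row event.**
- 5.2.6: no 7-day report.
- 5.2.7: no protocol-required IRB report and no CTEP-AERS report to forward.
- 9.4: outside the monthly notifications, which use the same label of unexpected.

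**Step 5: what still happens.**
- 5.2.1: the event is entered in Rave as routine reporting.
- 7.1: adverse events are assessed at Day 1 of each cycle.
- 9.4: toxicity is analysed twice yearly.
- 13: cumulative CDUS data go to CTEP quarterly, although the section does not state their adverse-event content.
- 5.2.6 and 5.2.8: grade 5 events, events causing persistent or significant disability, congenital anomaly or birth defect (footnote b), and secondary malignancies are expedited whatever their expectedness.

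**The case against.** The strongest reply is that the operative instructions may lie elsewhere. Section 5.2.5 is the step-by-step procedure for deciding on expedited reporting; only its heading can be read in the available text, and a figure nearby is not shown. Those steps may tell sites to consider both attributes. This stands as a limit on the conclusion, and the absence of that text is not an error in the plan. It does not remove the point, because a definition in 5.2.2 that disagreed with 5.2.5 would still need correcting.

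A second reply is that both drugs are commercial, and their labels may describe grade 4 for many of the listed types. For those events the connective makes no difference. This also stands, and it is why the number of affected events is left open.

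A third reply is that other safeguards operate without expectedness, as set out in the last step of the working. That is right, and it confines the gap to how quickly an event is circulated and to whom.

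Three stronger readings are tempting, and the documents support none of them.
- A reader might infer from the length of the two lists that almost any related grade 4 event would be classed as expected. The lists do not show this. Counting terms does not measure coverage of grade 4 events, and several serious events, such as myocardial infarction and pulmonary embolism, are not named in them.
- A reader might infer that a missed event stays unseen until the next twice-yearly review, and multiply that interval by the accrual rate to get the patients affected. That product would be a worst-case count of enrolments, not of patients harmed, and it ignores the routine channels.
- A reader might infer from the 30-patient retrospective series in 1.3, with grade 3 or 4 events in 4 patients, that undescribed severity is the chief unknown for the combination. That figure pools grades 3 and 4 and does not rank the sources of risk.

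**Conclusion.** The point holds in a limited form. As written, 5.2.2 and 5.2.6 together exempt from expedited reporting a treatment-related grade 4 event whose type is listed but whose severity is described in no reference document. The same event then falls outside the monthly notifications in 9.4 and the IRB reporting in 5.2.7. Because 8.1.10 and 8.2.10 carry no grades, this can arise for any type they list.

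The size cannot be given as a number of events. That would need the product labels and any brochure, which are not available, and sight of 5.2.5. The conclusion assumes that 5.2.5 does not override the definition and that sites apply 5.2.2 as it reads. The consequence is a delay and narrower circulation for some related grade 4 events; the data themselves still reach Rave. No endpoint, sample size, power or error rate is affected. It should be corrected because this is a stated rule that weakens the safety channel, and the correction is small.

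**What to change.** In 5.2.2, define an event as expected only when both its type and its severity are consistent with the reference documents, and as unexpected when either is not. Add one sentence saying that where 8.1.10 or 8.2.10 lists a type without a severity, the product label decides whether that severity is expected. Check that 5.2.5, 5.2.6 and 9.4 use the same definition.

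The cost is a change of connective, one added sentence and a consistency check, plus some additional 7-day reports for related grade 4 events. How many cannot be estimated from the documents. Grade 4 events whose type and severity are already described in the references would remain exempt, so the reporting load would not extend to all related grade 4 events.

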### 5.2.3 Reporting procedure

This study requires that expedited adverse event reporting use CTEP's Adverse Event Reporting System (CTEP-AERS). CTEP's guidelines for CTEP-AERS can be found at <http://ctep.cancer.gov>. A CTEP-AERS report must be submitted electronically to ECOG-ACRIN and the appropriate regulatory agencies via the CTEP-AERS Web-based application located at <http://ctep.cancer.gov>.

In the rare event when Internet connectivity is disrupted a 24-hour notification is to be made by telephone to

- the AE Team at ECOG-ACRIN [contact])
- the FDA [contact])

An electronic report **MUST** be submitted immediately upon re-establishment of internet connection.

Rev. 6/14

**Supporting and follow up data:** Any supporting or follow up documentation must be uploaded to the Supplemental Data Folder in Medidata Rave within 48-72 hours. In addition, supporting or follow up documentation must be faxed to the FDA [contact]) in the same timeframe.

**NCI Technical Help Desk:** For any technical questions or system problems regarding the use of the CTEP-AERS application, please contact the NCI Technical Help Desk at [[contact]](mailto:[contact]) or by phone at [name].

[figure not shown]
#### 5.2.4 Determination of reporting requirements

Many factors determine the reporting requirements of each individual protocol, and which events are reportable in an expeditious manner, including:

- the phase (0, 1, 2, or 3) of the trial
- whether the patient has received an investigational or commercial agent or both
- the Common Terminology Criteria for Adverse Events (CTCAE) grade
- the relationship to the study treatment (attribution)
- the expectedness of the adverse event

**Using these factors, the instructions and tables in the following sections have been customized for protocol E2211 and outline the specific expedited adverse event reporting requirements for study E2211.**

5.2.5 Steps to determine if an adverse event is to be reported in an expedited manner

5.2.6 Expedited Reporting Requirements for Arms A and B on protocol E2211

Commercial Agents: Temozolomide and Capecitabine

Expedited reporting requirements for adverse events experienced by patients on arm(s) with commercial agents only – (Arms A and B)					
Attribution	Grade 4		Grade 5 a		ECOG-ACRIN and Protocol-Specific Requirements
	Unexpected	Expected	Unexpected	Expected	
Unrelated or Unlikely			7 calendar days	7 calendar days	See footnote (b) for special requirements.
Possible, Probable, Definite	7 calendar days		7 calendar days	7 calendar days	

**7 Calendar Days:** Indicates a full CTEP-AERS report is to be submitted within 7 calendar days of learning of the event.

**a** This includes all deaths within 30 days of the last dose of treatment regardless of attribution. **NOTE: Any death that occurs > 30 days after the last dose of treatment and is attributed possibly, probably, or definitely to the treatment must be reported within 7 calendar days of learning of the event.**

**b** Protocol-specific expedited reporting requirements: The adverse events listed below also require expedited reporting for this trial:

**Serious Events:** Any event following treatment that results in *persistent or significant disabilities/incapacities, congenital anomalies, or birth defects* must be reported via CTEP-AERS within 7 calendar days of learning of the event. For instructions on how to specifically report these events via CTEP-AERS, please contact the AEMD Help Desk at [[contact]](mailto:[contact]) or [contact]. This will need to be discussed on a case-by-case basis.

5.2.7 Other recipients of adverse event reports and supplemental data

ECOG-ACRIN will forward CTEP-AERS reports to the appropriate regulatory agencies and pharmaceutical company, if applicable.

Adverse events determined to be reportable via CTEP-AERS must also be reported by the institution, according to the local policy and procedures, to the Institutional Review Board responsible for oversight of the patient.

